FWA	Federalwide Assurance
HIPAA	Health Insurance Portability and Accountability Act
ICF	Informed Consent Form
IRB	Institutional Review Board
MOP	Manual of Procedures
N	Number (typically refers to participants)
NIH	National Institutes of Health
NJSS	Nurse Job Satisfaction Survey
NYULH	NYU Langone Health
OHQ	Oxford Happiness Questionnaire
OHRP	Office for Human Research Protections
OHSR	Office of Human Subjects Research
PI	Principal Investigator
QA	Quality Assurance
QC	Quality Control
SAE	Serious Adverse Event/Serious Adverse Experience
SOP	Standard Operating Procedure
US	United States

CONFIDENTIAL

This material is the property of the NYU Langone Health. Do not disclose or use except as authorized in writing by the study sponsor

Protocol Summary

Title	Impact of visual arts immersion on cultural competency and self-reflection among nurses working in an academic health system
Short Title	Impact of visual arts immersion
Brief Summary	The purpose of this study is to enhance engagement, coping and self-reflection by attuning nurses to creative and observational skills drawn from a visual arts pedagogical framework. To fulfill this goal, we will cultivate an existing relationship between NYULH Nursing, the NYU Health Sciences Library, and museum educators at The Met to design and deliver an intervention of museum educator-led workshops that introduce nurses to arts appreciation skills to improve their practice and overall wellbeing. Participants will be asked to complete two surveys, pre- and post-intervention, Cultural Awareness Scale (CAS), which measures cultural awareness, sensitivity, knowledge and skills, and the Interpersonal Reactivity Index (IRI), which measures four separate aspects of empathy and its relationships with measures of social functioning, self-esteem, emotionality, and sensitivity to others. We will also solicit qualitative feedback via REDCap survey at the end of the intervention to gain insight into nurse's experiences of the art immersion program.
Objectives	The main objective is to determine if a visual arts educational intervention impacts nurse cultural competency and personal reflection skills. Secondary objective is to assess the feasibility of art immersion techniques for nurses as a broader pedagogical frameworks. We will solicit nurses' qualitative feedback about this aspect of the program.
Methodology	Mixed methods, quantitative pre-post survey and qualitative survey
Endpoint	The endpoint is 7 months from recruitment to final intervention session. The secondary endpoint is a further 3 months for completion of analysis and identification of findings.
Study Duration	The study will take 7 months to complete
Participant Duration	Subject participation will last 7 months from enrollment, to receive two arts education sessions.
Population	Participants will be drawn from the population of NYULH nurses on all campuses.
Study Site	NYULH
Number of participants	Up to 60 participants to be enrolled across NYULH campuses.
Statistical Analysis	Descriptive and inferential statistics will be used to analyze the data. Descriptive statistics will be used to describe the sample demographics. Dependent samples t-tests will be used to assess correlations and differences across time for the CAS and IRI surveys. Convergent analytic techniques will be used to link qualitative feedback to the quantitative survey results.

CONFIDENTIAL

This material is the property of the NYU School of Medicine and Langone Medical Center. Do not disclose or use except as authorized in writing by the study sponsor

Key Roles

[name], MSIS

Lead, Programming and Clinical Support, NYU Health Sciences Library, NYU Langone Health
[name]
Office: [contact]
[contact]

[name] [name], CCRN, CEN, ACNS-BC, FAEN, FCNS

System Senior Director of Nursing Research and Program Evaluation, NYU Langone Health
[name]
Office: [contact]
[contact]
[contact]

[name]

Research Coordinator, Center for Innovations in the Advancement of Care (CIAC), NYU Langone Health
[name]
Office: [contact]
[contact]

1 Introduction, Background Information and Scientific Rationale

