3.1 Description of Study Design

This is a single-site mixed methods longitudinal cohort with a pre-post measurement design. All NYULH registered nurses will be invited to participate. The purpose of this study is to enhance engagement, coping and self-reflection by attuning nurses to creative and observational skills drawn from a visual arts pedagogical framework. To fulfill this goal, we will cultivate an existing relationship between NYULH Nursing, the NYU Health Sciences Library, and museum educators at The Met to design and deliver an intervention of museum educator-led workshops that introduce nurses to arts appreciation skills to improve their practice and overall wellbeing.

Participants will be asked to complete two surveys, pre- and post-intervention, the Cultural Awareness Scale, which measures cultural awareness, sensitivity, knowledge and skills, and the Interpersonal Reactivity Index, which measures four separate aspects of empathy and its relationships with measures of social functioning, self-esteem, emotionality, and sensitivity to others. We will also solicit qualitative feedback via REDCap survey at the end of the intervention to gain insight into nurse's experiences of the art immersion program. All data will be analyzed in aggregate by the research coordinator and therefore no identifiable information will be available.

Descriptive and inferential statistics will be used to analyze the data. Descriptive statistics will be used to describe the sample demographics. Dependent samples t-tests will be used to assess correlations and

CONFIDENTIAL

This material is the property of the NYU Langone Health. Do not disclose or use except as authorized in writing by the study sponsor

Observational Study Template Version: 18 July 2022

differences pre- and post-intervention for the CAS and IRI surveys. Convergent analytic techniques will be used to link qualitative feedback to the quantitative survey results.

4 Study Enrollment and Withdrawal

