4.7.2 Handling of Participant Withdrawals or Termination

Participants who wish to withdraw may do so at any time with no consequence to their employment. There is no need to notify the PI, they may cease participation in the program or decline to complete surveys at their own discretion.

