5.5 Withdrawal Visit

No visit is required for withdrawal, participant may cease participation at any time

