6.1 Procedures/Evaluations

After consent has been obtained, the following will take place:

- Participants will be asked to provide their email or cell phone of choice so we may communicate study information, reminders, and surveys via email or text message.
- Participants will then be asked to complete a demographic survey, the Interpersonal Reactivity Index (IRI) and the Cultural Assessment Survey (CAS).
 - The demographic survey contains questions about age, race/ethnicity, gender, years of nursing experience, NYULH campus, specialty, shift time, and role (clinical or nurse leader).
 - CAS measures cultural awareness, sensitivity, knowledge and skills.
 - IRI measures four separate aspects of empathy and its relationships with measures of social functioning, self-esteem, emotionality, and sensitivity to others.
- Following completion of the surveys, participants will be asked to sign up for 2 art immersion classes. Participants will be offered 4 dates to sign up for the art immersion classes. An additional set of one in-person class and one virtual class will be added due to low enrollment. The first class will be an in-person class at the Metropolitan Museum of Art (MET) located on [name]. The second class will be virtual via WebEx. Each class will last 60 minutes.
- There will also be an optional independent self-directed reflective exercise with art materials and prompts provided by the MET.
- At 7 months (after second class), participants will be asked to complete the IRI and the CAS surveys again. Participants will also be asked to complete a short qualitative survey about the overall impact of the art immersion program on your work and life.

Museum educators from The MET will be providing the curriculum that will include an art immersion program that will select specific works/art in the museum as well as virtually that will help to stimulate self-reflection and prompt connection to their nursing practice. MET staff will be conducting workshops as part of their paid job and will not be engaged in human subjects research as researchers.

7 Adverse Events

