9.1 Study Hypotheses

Primary: Visual arts training by museum educators is associated with increased skills in cultural competency and personal reflection among nurses in clinical practice in an academic health system.

Secondary: Nurses believe training in the visual arts impacts their clinical practice and whether it can be widely applied to pedagogical nursing practice in an academic health system.

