9.2 Sample Size Determination

The target sample size is 60 NYULH nurses. Sample size calculations were performed in G*Power with the following parameters

- Test statistic: Dependent samples t-test
- Effect size estimation=0.4
- Type I error probability=0.90
- Type II error probability=0.05

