9.3 Statistical Methods

Demographics will be reported with descriptive statistics including means and frequency counts.

The main objective, to determine whether visual arts training by museum educators increases nurses' skill in cultural competency and personal reflection, will be assessed with a dependent samples t-test. We will compare CAS and IRI at baseline and post-program to find if there is a significant difference in mean scores.

The secondary objective, to understand nurse beliefs about the pedagogical value of visual arts education to nursing practice, will be explored via qualitative survey (attached as separate document) and thematically analyzed.

10 Source Documents and Access to Source Data/Documents

REDCap will be the primary data collection instrument for the study.

Access to study records will be limited to IRB-approved members of the study team. The PI will permit study-related monitoring, audits, and inspections by the IRB, the sponsor, government regulatory bodies, and University compliance and quality assurance groups of all study related documents (e.g. source documents, regulatory documents, data collection instruments, study data etc.). The PI will ensure the capability for inspections of applicable study-related facilities.

Participation as an investigator in this study implies acceptance of potential inspection by government regulatory authorities and applicable University compliance and quality assurance offices.

11 Ethics/Protection of Human Subjects

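### Does the completers-only paired t-test need added non-response analyses, given that nurses may drop out silently?

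*Combined protocol and SAP*

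**What the plan says.** The Statistical Analysis row of the Protocol Summary says that "Dependent samples t-tests will be used to assess correlations and differences across time for the CAS and IRI surveys". Section 3.1 repeats this ("Dependent samples t-tests will be used to assess correlations and" differences before and after the intervention). Section 9.3 says that the main objective "will be assessed with a dependent samples t-test. We will compare CAS and IRI at baseline and post-program". Everything else in the analysis is descriptive, thematic or a linkage of qualitative to quantitative results.

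On stopping, section 4.7.2 says: "There is no need to notify the PI, they may cease participation in the program or decline to complete surveys at their own discretion". Section 5.5 adds: "No visit is required for withdrawal, participant may cease participation at any time". Section 6.1 puts the baseline surveys before class booking: "Following completion of the surveys, participants will be asked to sign up for 2 art immersion classes". It places the repeat surveys after the second class.

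Section 9.1 states the hypothesis as "Visual arts training by museum educators is associated with increased skills in cultural competency and personal reflection among nurses in clinical practice". Section 9.2 says "The target sample size is 60 NYULH nurses" and gives an effect size of 0.4. Section 4.6 makes 60 an upper limit, and sections 4.4, 5.3 and 6.1 record that enrolment has been low.

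**The concern.** A paired t-test needs two scores per nurse. A nurse who completes the baseline and then books no class, or ignores the final survey link, drops out of the only inferential result. The protocol allows this without notice or a reason. It states no analysis population, no missing-data rule, no comparison of responders with non-responders and no sensitivity analysis. Nor does it say whether the mean change is meant for all enrolled nurses or for those who took the classes.

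The study has one group, so mean change on the Cultural Awareness Scale (CAS) and the Interpersonal Reactivity Index (IRI) is its whole quantitative answer. If nurses who gained more were also more likely to reply, the completers' mean would overstate the benefit, and nothing written in the plan would reveal it. The natural response is to ask for an all-baseline repeated-measures model, a responder comparison and a delta-adjusted stress test. The Summary and section 3.1 also give the t-test the job of assessing correlations, whereas it assesses a mean difference.

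**Working it through.** **Inputs from the documents.** Paired t-test; effect 0.4, read as the mean change divided by the SD of change; target and cap of 60.

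**Assumptions, because the documents give no figure.** Loss of 20% or 30% (48 or 42 pairs if 60 enrol); pre-post correlation r of 0.5-0.7; a 5% level. Section 9.2 prints a Type I error of 0.90 and a Type II error of 0.05, which look like swapped labels for 90% power and a 5% level. Sidedness is not stated.

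**Step 1: the plan's own figure.** By the noncentral t distribution, effect 0.4, alpha 0.05 and power 0.90 need 55 pairs one-sided or 68 two-sided, so 60 is not reproduced exactly. Sixty pairs give power of 92.2% one-sided or 86.2% two-sided. With 48 pairs these are 86.1% and 77.5%; with 42 pairs, 81.7% and 71.6%.

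**Step 2: is the paired test worse than the proposed model?** Simulation with 60 nurses and 40,000 replicates per scenario:

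- pre = √r·T + √(1−r)·e1
- post = δ + √r·T + √(1−r)·e2, with δ = 0.4·√(2(1−r))
- the log-odds of replying rise by 0.5 or 1 per SD of the driver named below

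Absolute bias as a share of δ, over r, loss and slope:

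| Reply depends on | Paired t-test | Likelihood model, all baselines |
|---|---|---|
| nothing | at most 0.3% | at most 0.3% |
| baseline score | 9-31% | under 1% |
| stable level T | under 1% | 8-24% |
| post score | 9-32% | 16-49% |
| the change itself | 24-63% | 18-55% |

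Each of the four drivers has 3 correlations × 2 loss rates × 2 slopes = 12 scenarios. The model's root mean squared error is lower in all 12 for baseline and all 12 for change. It is higher in all 12 for post score and all 12 for stable level: 24 against 24.

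**Step 3: how far could non-responders move the answer?** Let m be the share lost and g the non-responders' mean change in SD units. If completers show 0.40, the all-enrolled change is 0.40(1−m) + m·g.

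- Completers alone: t = 0.40·√42 = 2.59, p = 0.013; t = 0.40·√48 = 2.77, p = 0.008 (two-sided).
- g = 0, 30% loss: effect 0.40 × 0.70 = 0.28. Multiple imputation with Rubin's rules gives t = 1.80-1.83; p = 0.074-0.079 two-sided, 0.037-0.040 one-sided. Two-sided significance is lost below g of about 0.09-0.11.
- g = 0, 20% loss: effect 0.40 × 0.80 = 0.32, t = 2.20-2.23, p = 0.031-0.033 two-sided. Significance is lost only with g between −0.1 and −0.2.

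**Step 4: dependence on reaching 60.** If 30 enrolled (an assumption), the same loss leaves 24 or 21 pairs. Then t = 0.40·√24 = 1.96, p = 0.062, or t = 0.40·√21 = 1.83, p = 0.082. There would be no significant two-sided result to stress-test.

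**The case for a change.** The strongest case for adding analyses is that the loss is foreseeable and could create a false positive. With a true mean change of zero and an assumed correlation of 0.2-0.5 between a nurse's change and her tendency to reply, the completers' two-sided 5% test rejects in 7.5-23.6% of simulated studies at 20% loss and 9.1-38.7% at 30%. Baseline CAS, IRI and demographics are collected anyway, the text would be short, and settling the method before the results are seen prevents a choice afterwards.

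The factual part of this stands: silent loss is allowed, the plan is silent on it, and the mean could be biased. As a case for changing the plan it is weaker, for four reasons.

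- The correlation is assumed, and no analysis of two time points can identify it. When reply depends on the change itself, the all-baseline model is still biased by 18-55%.
- Comparing baselines has limited power. With 42 repliers and 18 non-repliers, a 0.5 SD difference would be detected 42% of the time; with 48 and 12, 33%. A null result could falsely reassure.
- The stress test changes the conclusion only under some readings: 30% loss, two-sided, with the cap of 60 reached.
- An all-baseline analysis presupposes that every enrolled nurse is the target. The hypothesis concerns training and the final survey follows the second class, so class-takers are a plausible target. Section 4.3 says that no data are collected at the sessions, so that target would need an attendance record the plan does not describe.

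**Conclusion.** The concern describes a real silence, but it does not show an error in the plan. The paired t-test is a standard analysis for one baseline and one follow-up, and even the case for more analysis keeps it as primary. It estimates mean change among nurses with both surveys, and its degrees of freedom disclose how many there were. The main alternative trades one set of assumptions for another: better in 24 scenarios, worse in 24.

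What remains is an unwritten missing-data policy. An analyst would ordinarily report how many nurses answered each survey, describe the baseline scores and demographics of those who did not reply, and confine the conclusion to nurses with both surveys. The data for this exist without a change to the plan. The mention of correlations is a slip of wording, because section 9.3 states the comparison correctly as a difference in mean scores.

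The sizes rest on assumed loss of 20-30%, r of 0.5-0.7, an effect of 0.4 read as standardised change, and 60 enrolled, which is a cap in a study with recorded low enrolment. Heavy loss, or clear signs that replying followed perceived benefit, would make a stress test worth reporting. A pre-post study without a control group cannot in any case separate the program's effect from time or repeat testing, whatever is done about missing surveys.

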1.1 Background Information and Relevant Literature

Nurses comprise the largest segment of the healthcare workforce both nationally and within our urban multi-site academic health system (AHS). Over 4 million registered nurses live and work in the United States and over 9,000 nurses work in this multi-site AHS. Nurses work in modern environments of escalating complexity, facing significant time pressures, staffing challenges and increased patient acuity. They face a myriad of emotional and occupational challenges that affect the nursing workforce, contributing to a cascading crisis in the healthcare workplace through staffing turnover. High stress and nurse burnout result in lower quality and safety of patient care (Keykaleh 2018). It is incumbent upon healthcare organizations to mitigate burnout by supporting overall employee wellbeing. While there are many approaches to activating employee engagement, this program specifically utilizes techniques of engaged observation through visual arts instructional techniques to help nurses hone their skills of perception and to reconnect to their practice. The World Health Organization defines stress to be the “body's response to anything that requires attention or action” (WHO 2022) and clinical workplaces are stressful environments of interruption, urgency and shifting attention. More than ever, nurses need proficiency using in techniques, skills and interventions supporting personal health behaviors and wellness.

1.2 Rationale

The overall goal of this project is to enhance engagement, resilience and cultural competence by introducing nurses to skills drawn from a visual arts pedagogical framework. Through reflective, experiential approaches nurses will be introduced to museum works by an expert educator and guided through interactive exercises and discussions. Though many academic papers describe visual arts frameworks used among nursing students, few describe using this format among nurses in practice with a validated cultural competence instrument.

CONFIDENTIAL

This material is the property of the NYU Langone Health. Do not disclose or use except as authorized in writing by the study sponsor

Observational Study Template Version: 18 July 2022

1.3 Potential Risks & Benefits

1.3.1 Known Potential Risks

The risk of being identified as participating in the study will be minimized by not collecting participant names. All collected information will be placed in REDCap. Once the study is complete emails and cell phone numbers will be destroyed. All de-identified data will be analyzed and reported in aggregate to decrease the chance of being identified. Participants can choose to withdraw from the study at any point.

1.3.2 Known Potential Benefits

Participants may or may not develop increased self-reflective skills that benefit performance and awareness of connections in nursing practice. The results of this study will help to guide future interventions to assist nurses in developing self-reflective and cultural competency skills that translate to the workplace setting.

2 Objectives and Purpose

2.1 Primary Objective

The main objective is to determine if a visual arts educational intervention impacts nurse cultural competency and personal reflection skills.

2.2 Secondary Objectives

The secondary objective is to understand if nurses believe training in the visual arts impacts their clinical practice and whether it can be widely applied to pedagogical nursing practice.

3 Study Design and Endpoints

3.1 Description of Study Design

This is a single-site mixed methods longitudinal cohort with a pre-post measurement design. All NYULH registered nurses will be invited to participate. The purpose of this study is to enhance engagement, coping and self-reflection by attuning nurses to creative and observational skills drawn from a visual arts pedagogical framework. To fulfill this goal, we will cultivate an existing relationship between NYULH Nursing, the NYU Health Sciences Library, and museum educators at The Met to design and deliver an intervention of museum educator-led workshops that introduce nurses to arts appreciation skills to improve their practice and overall wellbeing.

Participants will be asked to complete two surveys, pre- and post-intervention, the Cultural Awareness Scale, which measures cultural awareness, sensitivity, knowledge and skills, and the Interpersonal Reactivity Index, which measures four separate aspects of empathy and its relationships with measures of social functioning, self-esteem, emotionality, and sensitivity to others. We will also solicit qualitative feedback via REDCap survey at the end of the intervention to gain insight into nurse's experiences of the art immersion program. All data will be analyzed in aggregate by the research coordinator and therefore no identifiable information will be available.

Descriptive and inferential statistics will be used to analyze the data. Descriptive statistics will be used to describe the sample demographics. Dependent samples t-tests will be used to assess correlations and

CONFIDENTIAL

This material is the property of the NYU Langone Health. Do not disclose or use except as authorized in writing by the study sponsor

Observational Study Template Version: 18 July 2022

differences pre- and post-intervention for the CAS and IRI surveys. Convergent analytic techniques will be used to link qualitative feedback to the quantitative survey results.

4 Study Enrollment and Withdrawal

